Examining the Active Ingredients of Consultation to Improve Implementation of a Parent-mediated Intervention for Children With Autism in the Community Mental Health System

NCT04654117

06/17/2024

This study will examine which components of consultation are most helpful in improving clinical services that community providers deliver to Medicaid-enrolled children with autism spectrum disorder (ASD). Specifically, the project will focus on parent-mediated intervention, which is a best practice for improving skills in children with autism spectrum disorder. Previous work from our research team demonstrated very low frequency of billing claims for parent-mediated intervention within the Medicaid Autism Benefit – nearly half of children had not received a parent-mediated intervention session over the course of 6 months, and only 2.7% received parent-mediated intervention at a frequency that is consistent with evidence-based models (Straiton et al., 2021a). Qualitative data illustrated that providers are also largely unaware of evidence-based components of parent-mediated intervention sessions (e.g., care-giver practice with feedback). Our work highlighted that providers in this system are underprepared to deliver parent-mediated interventions and perceive numerous barriers at the family-, provider-, and agency-levels (Straiton et al., 2021b), such as perceived limited engagement and interest from caregivers, limited provider training, and competing demands on providers' time. This research demonstrated that providers desired training in the delivery of a manualized parent-mediated intervention that could be delivered via telehealth during the pandemic to address social communication deficits in children with ASD (Project ImPACT). The current project will address this need by supporting providers in this same system to use a manualized parent-mediated intervention with their clients with ASD. We will also be able to examine which components of consultation are most helpful in supporting providers to use this best practice within this system.

Specific Aim 1: Identify the potential active ingredients of the consultation model by evaluating its effects on providers' treatment adherence and parent-mediated intervention competence. I

predict that the feedback component will improve adherence and competence over and above improvements from the case support and skill rehearsal components.

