Baseline lengths were randomized by a statistician unaware of agency characteristics using a random-number generator. Published standards for single-case designs require a minimum of 3 observations per phase to “meet standards with reservations” (Kratochwill et al., 2013). See Table 2 for the baseline lengths for each agency. Baseline lengths for agencies 1-4 were randomized for 3-6 weeks. Due to a methodological challenge (outlined below), baseline lengths for agencies #5 and #6 were randomized for 6-9 weeks to ensure that clinicians had sufficient baselines.

Consultation phase. Group consultation sessions took place via a teleconference platform (Zoom). During a given consultation condition (i.e., 4-week block in which only one consultation training activity was delivered), no components of any other conditions were provided. For example, during the skill rehearsal condition, no feedback was given about the role

plays, so that the only performance feedback clinicians received occurred in the feedback condition. All providers received each of the 3 consultation conditions (i.e., training activities), with each training activity delivered in isolation for a given 4-week consultation period. The order in which providers received each component was randomized for each agency by a statistician unaware of agency characteristics using a random-number generator, such that each agency had an equal chance of receiving one of the predetermined permutations of conditions (e.g., equally as likely to be randomized to ABCD order as ADCB order). Consultation sessions were rescheduled for the following week if more than half of participants at an agency would not be present or if the consultant would not be present. See Table 2 for the consultation component order for each agency.

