Methodological challenge with the baseline phase. The research team became aware of a methodological flaw following visual analysis of manual adherence data from the first 4 agencies. Within-condition visual analysis indicated that baselines across agencies were unstable due to inflation of the manual adherence scores for the first 2 sessions of Project ImPACT, as compared to sessions 3-24. Conceptually, this made sense because these 2 sessions were atypical and did not include instruction on NDBI techniques nor an active parent coaching component in which clinicians provided feedback; session 1 was an overview of the program and session 2 was a goal setting session. Both sessions are much less complex than the other parent coaching sessions. Agencies #1-4 had started data collection by this point, and due to the initial randomization procedure using parameters of 3-6 weeks of baseline, only 1 agency had at least 3 weeks of usable baseline sessions (Agency #2). For this reason, an additional 2 agencies were recruited (Agencies #5 and #6), and baseline lengths for those agencies were randomized for 6-9 weeks to ensure that baseline lengths had at least 3 usable Project ImPACT sessions. Additionally, to allow for the retention of all clinicians in Agencies #5 and #6, baselines for those two agencies were extended by 1 week to allow for clinicians who had multiple cancellations in the baseline period to acquire at least 2 usable baseline sessions.

Consultant Fidelity to Consultation Conditions

Consultant fidelity to the three consultation conditions was assessed by 2 coders naïve to condition and timepoint using the Project ImPACT Consultation Adherence Checklist. The checklist included scores for the percentage of required training activities for each of the 3 consultation components, as well as the length of time spent on the training activities (e.g., time

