Manual adherence. Adherence to the Project ImPACT manual content was assessed by coders naïve to session number or timepoint via the Project ImPACT Coaching Fidelity Checklist (Ingersoll & Dvortcsak, 2019) to identify the extent to which clinicians adhered to lesson plans and content from the manual. Items include appropriate use of Project ImPACT program materials (e.g., use of handouts and the parent manual), appropriate description of Project ImPACT NDBI techniques to caregivers, sufficient time spent on critical Project ImPACT session components (e.g., at least 12 minutes of caregiver practice time), and presence of parent coaching clinical skills (e.g., provision of effective positive coaching feedback). Certain items that are considered more central to a parent coaching approach are weighted heavier (e.g., sufficient caregiver practice time, providing corrective feedback to caregivers), whereas other items are weighted less (e.g., assigning reading for the next session as homework). Clinically, a score of 80% or higher on this measure is considered “at fidelity.” All Project ImPACT sessions were randomly assigned to be scored by two independent coders naïve to timepoint and condition. Coders needed to meet training criteria of 3 videos in a row with 80% of items in exact agreement with the master coder prior to coding for the actual dataset. Monthly meetings with the coding team were held in which all members independently coded a video, and the group compared their scores to the master codes and discussed discrepancies. Once trained, coders met to discuss each videotaped session and resolved any disagreements by consensus. Consensus scores were used in the final analyses.

Parent coaching competency. Competency in parent coaching was assessed by coders naïve to session number or timepoint via the Parent Empowerment and Coaching in Early Intervention (PEACE) measure (Pellecchia et al., 2023) which utilizes a 5-point Likert scale to assess quality and competency in delivering collaborative coaching techniques used in parent-

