Statistical Analysis. An overview the statistical analysis used for each aim is presented in this section. Recent advances in statistical modeling have resulted in the specification of multilevel models that can provide effect sizes for each treatment element while also accounting for the specific features of single-case experimental designs (e.g., handling auto-correlation among consecutive datapoints, correcting for design-specific error structures). These advances have resulted in statistical packages in the R statistics platform (e.g., *sdhlm*). These tools were used to analyze results for Aims 1, 3, and 4. Specific model parameters are presented in the Results section.

Multilevel modeling for Aim 1: Effects of the group consultation model and each consultation component on clinician manual adherence and parent coaching competency. Only data from the 3 agencies with sufficient baseline data were used for Aim 1 analysis. We examined the effects of individual components of the group consultation model (i.e., consultation training activities) on clinician fidelity (i.e., manual adherence, parent coaching competency). To do so, we utilized 2-level multilevel models to estimate the change in level from the average baseline fidelity score to the average fidelity level for each consultation training activity condition (i.e., changes in level from baseline to each consultation condition). For example, the model estimated the magnitude of change from the Baseline level to the Feedback level, and whether the change was statistically significant. Specific model parameters for all models are presented in the Results section.

The models provide two sets of estimates: 1) the average effect of each consultation component on fidelity scores *averaged across clinicians* (i.e., results from the 2-level model),

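### The Aim 1 prediction compares Feedback with the other two components, so a short baseline is no reason to leave Agencies 1, 3 and 4 out of that contrast

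*Combined protocol and SAP*

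**What the plan says.** Under Specific Aim 1 the investigator writes: "predict that the feedback component will improve adherence and competence over and above improvements from the case support and skill rehearsal components". The Consultation phase section says that every agency had its component order randomised.

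The visual analysis and the multilevel model for Aim 1 carry the same restriction: "Only data from the 3 agencies with sufficient baseline data were used for Aim 1 analysis". The model is described as estimating the change from the average baseline level to the level in each of the three conditions. No contrast between components is described, and the model parameters are left to a Results section that is not part of the document.

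The reason for the restriction is in the section on the methodological challenge with the baseline phase. Project ImPACT sessions 1 and 2 gave inflated adherence scores and had to be set aside. "Baseline lengths for agencies 1-4 were randomized for 3-6 weeks", and of those four only Agency 2 still had 3 usable baseline weeks, so Agencies 5 and 6 were recruited with longer baselines. The threshold comes from the single-case literature: "Published standards for single-case designs require a minimum of 3 observations per phase".

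On data availability, the Design overview says that clinicians submitted recordings of all sessions in the baseline and consultation phases. The Manual adherence section adds: "All Project ImPACT sessions were randomly assigned to be scored by two independent coders naïve to timepoint and condition". The Parent coaching competency section assigns all sessions to one primary coder. Aims 2 and 3 use all 6 agencies and Exploratory Aim 4 uses 5.

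**The concern.** The restriction protects comparisons that start from baseline. The prediction compares conditions that the same clinicians all went through, and a weak baseline does not weaken that comparison. As written, the plan estimates three baseline-to-condition changes and sets out no test of the stated prediction. It also applies to the whole of Aim 1 an exclusion that only the baseline comparisons need.

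Two things are at stake. One is precision in a small study: the plan says the sample was too small even for an agency level in the model. The other is coverage of component orders. Three agencies can show at most 3 of the 6 possible orders, so a component's apparent effect is hard to separate from the block in which it happened to fall.

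**Working it through.** **1. The plan's own count.** One usable agency among the first four (Agency 2), plus Agencies 5 and 6, gives 3 of 6. This reproduces the stated 3 agencies. The excluded ones are Agencies 1, 3 and 4.

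**2. Baseline cancels.** Let B, F, C and S be the mean fidelity levels at Baseline, Feedback, Case Support and Skill Rehearsal. Even if the prediction is read as a comparison of improvements from baseline,

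(F − B) − [(C − B) + (S − B)]/2 = F − (C + S)/2.

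**3. Does the plan's model behave this way?** The check used generalised least squares on the 2-level model described (clinician intercept plus a random effect per condition).
- From the documents: 60 models / 5 outcomes = 12 clinicians, which fits 3 agencies of 3-5 clinicians. Sessions per 4-week block: 4 × (1 − 76/299) = 2.98, taken as 3.
- Assumed: residual SD 1, intercept SD 1, condition-effect SD 0, 0.5 or 1, AR(1) 0 or 0.3.

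Standard error of F − (C + S)/2 for 12 clinicians:

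| Condition SD | AR(1) | 4 baseline sessions | No baseline sessions |
|---|---|---|---|
| 0 | 0 | 0.204 | 0.204 |
| 0.5 | 0 | 0.270 | 0.270 |
| 1 | 0 | 0.408 | 0.408 |
| 0 | 0.3 | 0.232 | 0.234 |
| 0.5 | 0.3 | 0.292 | 0.293 |
| 1 | 0.3 | 0.423 | 0.424 |

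The difference is below 1% throughout. A clinician without usable baseline sessions gives essentially full information on this contrast.

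**4. Gain in precision, equal agency weights (assumed).** The standard error scales with 1/√(number of agencies):
- 3 to 5 agencies: √(3/5) = 0.775, a cut of about 23%.
- 3 to 6 complete agencies: √(3/6) = 0.707, a cut of about 29%. This is an upper limit, because one agency stopped at 6 of 12 sessions.

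Both figures take the 3 retained agencies as complete. The text does not say which agency stopped.

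**5. Cross-check by clinicians.** With 3-5 clinicians per agency:
- Two added agencies bring 6-10 clinicians: √(12/18) = 0.816 to √(12/22) = 0.739.
- Three bring 9-15: √(12/21) = 0.756 to √(12/27) = 0.667.

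The range is of the same order as in step 4.

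**6. Order coverage.** Three components have 3! = 6 orders. Twelve ordered triples place each component once in each block. If orders are drawn at random, the chance that 3 agencies are balanced in this way is 12/216 = 5.6% with replacement, or 12/(6 × 5 × 4) = 10% without. The actual orders are in the plan's Table 2, which was not available here, so the real coverage with 3 or 6 agencies was not checked.

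**7. Effect on the baseline-to-component estimates.** Suppose 12 clinicians with 0 or 1 baseline sessions join 12 with 4 (3 sessions per block, residual SD 1, intercept SD 0.5-2, condition SD 0-1, no autocorrelation). Then between about 1% and 32% of any overall level difference between the two groups passes into the baseline-to-Feedback estimate. None of it passes into F − (C + S)/2.

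**The case against.** The strongest reply is that the restriction fits the analysis the plan describes. Baseline-to-condition changes need a baseline, and so does the visual comparison of adjacent conditions when it starts from the baseline phase. The restriction is disclosed and explained. All of this stands, and step 7 shows that pooling all agencies for the baseline-to-component estimates could do harm. It does not reach the Feedback contrast.

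It also stands that order and carry-over can distort any comparison of components: training accumulates and no washout is described. But this affects the 3-agency set as well.

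A reader might infer more than the documents support, in three ways.
- *That agencies were selected on results.* Fidelity scores had been viewed, but the problem seen was unstable baselines. The plan gives a content reason (sessions 1 and 2 contain no technique instruction or active coaching) and traces the shortfall to the randomised baseline lengths. Nothing ties the exclusion to component effects.
- *That the plan breaks its own threshold*, because baselines at Agencies 5 and 6 were extended "to allow for clinicians who had multiple cancellations in the baseline period to acquire at least 2 usable baseline sessions". That figure is for individual clinicians. The 3-week criterion is applied to agencies, and the visual analysis uses weekly agency averages. The units differ, so no breach is shown.
- *That about half of the outcome data is discarded.* The consultation-session count (5 × 12 + 6 = 66) measures training delivered to clinicians. Aim 1 outcomes come from clinician-family sessions, and no count of those is given for the excluded agencies.

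**Conclusion.** The point holds in a limited form. The stated Aim 1 prediction has no described contrast, and the reason for excluding Agencies 1, 3 and 4 does not apply to that contrast. The 3-agency restriction is sound for the visual analysis and for the baseline-to-component estimates.

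The likely gain is a standard error smaller by about 23% with 5 agencies, and by at most about 29% with 6, together with possibly more component orders. These figures assume equal agency weights and complete retained agencies, and are before any cost of a position term. They also assume that consultation-phase sessions in the excluded agencies were scored as assigned. This is an inexpensive improvement in precision. It does not show that the planned estimates are biased.

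**What to change.** Keep the 3-agency set for the visual analysis and for the baseline-to-component estimates. Add to the multilevel modeling section for Aim 1:

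- the contrast Feedback minus the mean of Case Support and Skill Rehearsal, for each fidelity outcome;
- its data set: consultation-phase sessions from all agencies with scored sessions, leaving out Project ImPACT sessions 1 and 2;
- a term for block position (first, second or third);
- the same contrast from the 3 agencies, reported beside it;
- the all-agency result with and without the agency that stopped at 6 of 12 consultation sessions;
- the number of scored clinician-family sessions by agency and condition.

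The cost is a paragraph of analysis text and a further model run for each outcome, with no new data collection. The position term uses up some precision; how much depends on the orders in Table 2. It adjusts for average block effects but does not remove carry-over from one component to the next, which should be stated as a limitation.

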3 agencies with sufficient baseline data were used for Aim 1 analysis. A summative between conditions visual analysis was used to evaluate changes in data patterns (changes in level, trend, and variability from one condition to the adjacent condition; Barton et al., 2018, p. 190). We conducted a visual analysis for each agency (using weekly data averaged across all clinicians at the agency). Hypotheses about the presence of a functional relation were tentatively confirmed or rejected based on whether the consultation component was associated with a change in level from one condition to the subsequent condition. We hypothesized that consultation components would be associated with a change in level from condition to condition. Less emphasis was placed on trends and changes in trend direction because we did not have any hypotheses that scores would vary within a 4-week period due to the effect of time. Thus, change in level was the main indication of a significant finding; however, if there was a clear and meaningful shift in trend direction (e.g., steep decelerating trend to gradual accelerating trend but no change in mean level), this was also used when determining which phase changes were considered significant. This effect needed to be replicated across all 3 agencies (inter-case replication) for the functional relation to be tentatively confirmed; recommendations for interpreting single-case designs suggest that an effect should be replicated across at least 3 cases.

Ideally, a functional relation should be confirmed when there is evidence of both *intra*-case and *inter*-case replication (Barton et al., 2018). Resource limitations prevented our research design from demonstrating replicated effects within agencies (intra-case replication) – this would require multiple baseline phases and multiple conditions of each consultation component, resulting in a consultation period that would last well beyond the present 3-month duration and thereby make participant recruitment and retention unlikely. Therefore, any functional relations

that were identified in this study could only be labeled as “tentatively confirmed” if inter-case replication was found.

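### Aim 1 predicts that feedback improves fidelity beyond case support and skill rehearsal, but the multilevel analysis described tests each component only against baseline

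*Combined protocol and SAP*

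**What the plan says.** Specific Aim 1 seeks the active ingredients of consultation and makes one directional prediction. The investigator goes on to "predict that the feedback component will improve adherence and competence over and above improvements from the case support and skill rehearsal components".

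The Data Analytic Plan, under multilevel modeling for Aim 1, uses two-level models to "estimate the change in level from the average baseline fidelity score to the average fidelity level for each consultation training activity condition". Its example reads: "the model estimated the magnitude of change from the Baseline level to the Feedback level, and whether the change was statistically significant". The rest of that section lists one fixed effect per component, clinician random effects for the intercept and for each component, and clinician-specific estimates built from these. It adds: "Specific model parameters for all models are presented in the Results section".

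The visual analysis for Aim 1 looks at "changes in level, trend, and variability from one condition to the adjacent condition". Its hypothesis is: "We hypothesized that consultation components would be associated with a change in level from condition to condition". An effect must recur in all 3 analyzed agencies before a functional relation is provisionally accepted.

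On sequence, the description of the consultation phase says: "The order in which providers received each component was randomized for each agency".

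**The concern.** The prediction is about differences between components, whereas every estimate and test described in the model section is a difference from baseline. Results of that kind show whether each component is accompanied by a change. They do not show whether feedback adds more than the other two, and that is the question Aim 1 asks.

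The practical risk lies in interpretation. If feedback were significant against baseline and case support were not, a reader could take that as support for the prediction. It would not be: each result compares one component with a shared baseline, and neither compares the two components. The blocks are also delivered one after another, and no order or time term is described. In an agency where feedback comes last, its change from baseline can therefore include whatever remains from the two earlier blocks.

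**Working it through.** The plan gives no power, sample-size or effect figure for this comparison, so there is nothing to reproduce. The check matches the hypothesis to the quantities estimated, then asks what the visual analysis can contribute.

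**Step 1: the model.** Let dF, dC and dS be the mean changes from baseline under Feedback, Case Support and Skill Rehearsal. These are the three fixed effects described.

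- Aim 1 prediction: dF − dC > 0 and dF − dS > 0.
- Tests described: dF = 0, dC = 0, dS = 0, each against baseline.

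Suppose dF = dC = dS = d, with d > 0. The prediction is then false, yet all three baseline tests can be significant. Now suppose dF > dC > 0 and dF > dS > 0. The prediction is true, and all three can again be significant. The same set of baseline results fits both cases, so those results do not decide between them. A mixed pattern, with one component significant and another not, is no better, because it never tests a difference between components.

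The missing quantity comes from the same fit: the estimate is dF − dC, with variance Var(dF) + Var(dC) − 2 Cov(dF, dC). The same holds for dF − dS. Standard software returns both.

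**Step 2: how many contrasts.** The model section refers to 5 outcome variables, which matches manual adherence plus the four PEACE subscales. Two contrasts per outcome gives 2 × 5 = 10.

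**Step 3: the visual analysis.** Three components can be ordered in 6 ways. F is feedback, CS case support, SR skill rehearsal.

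| Order | Condition before feedback | Component(s) next to feedback |
|---|---|---|
| F, CS, SR | baseline | CS |
| F, SR, CS | baseline | SR |
| CS, F, SR | CS | both |
| SR, F, CS | SR | both |
| CS, SR, F | SR | SR |
| SR, CS, F | CS | CS |

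- The change into feedback starts from baseline in 2 orders, from case support in 2 and from skill rehearsal in 2.
- Counting changes out of feedback as well, feedback adjoins at least one other component in every order, and both in 2 of 6.

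Assume all 6 orders are equally likely and drawn independently for the 3 analyzed agencies, giving 6³ = 216 possible draws. Table 2, with the actual orders, is not in the supplied text.

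- Feedback adjoins each other component in at least one agency unless all three agencies fall in the two CS-only orders or all three fall in the two SR-only orders: 216 − 2 × 2³ = 200 of 216 draws (93%).
- Feedback adjoins both other components in all three agencies only if it is in the middle block every time: 2³ = 8 of 216 draws (4%).

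The visual analysis will therefore usually offer some direct comparison of feedback with each other component, but rarely both comparisons in all three agencies, which is the replication the plan requires. It also states no criterion by which feedback would be judged superior.

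**Step 4: how much information there is.** The plan counts 60 separate models for 5 outcomes across clinicians, so 60 / 5 = 12 clinicians, in 3 agencies.

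**The case against.** Four points can fairly be made for the plan.

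- **The section is an overview.** It describes itself that way and defers model parameters to the Results section. This stands. It can be shown that no contrast is described here, but not that none was computed. A reader might infer that the investigators never compared the components statistically; the documents do not support that.
- **The visual analysis is where hypotheses are accepted or rejected.** Comparing neighboring phases is arguably the closest thing in the plan to an added gain from feedback. This stands in part. In most randomizations some direct comparison exists, but the stated hypothesis is any change in level, feedback is not singled out, and no estimate or test results.
- **The differences are already implicit in the fitted models.** True: point differences follow by subtraction and no data are lost. A reader might infer that the design cannot answer the question, which would be too strong. What is missing is a contrast.
- **Nothing says superiority will be read from separate p-values.** Also true. A reader might infer that the plan adopts that rule and try to attach a false-positive rate to it. The documents state no such rule, so no error rate for this trial can be given.

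The plan is also cautious already: any functional relation is provisional at best. That caution concerns replication within agencies and does not supply the comparison between components.

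**Conclusion.** The mismatch is real and narrow. As described, the directional prediction in Aim 1 has no statistical test, and separate significance results against a shared baseline would not provide one. The shortfall is two contrasts for each of five outcomes. Its effect on any estimate cannot be sized, because the documents give no standard errors, effect sizes or variance components for Aim 1.

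The conclusion rests on reading the prediction as a comparison of feedback with each of the other two components, and on the model section as supplied. It would fall away if the Results section already reports these contrasts, so confidence is moderate. It is worth correcting because the remedy is nearly free and answers the question the aim poses.

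**What to change.** From the same fitted models, report Feedback minus Case Support and Feedback minus Skill Rehearsal, with 95% confidence intervals, for manual adherence and the four PEACE subscales. Base any statistical statement that feedback adds to the other components on both contrasts. If they are already in the Results section, cite them in the plan. If they are added after the data were seen, label them post hoc.

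If the contrasts are not reported, limit Aim 1's statistical conclusions to changes from baseline to each component, and say that the prediction about feedback was not tested statistically.

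Either way, state as a limitation that component differences cannot be fully separated from order and carry-over. A model term for block position is not required here; the plan itself notes that the sample was too small to add an agency level.

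The cost is two linear contrasts in each of five existing models and a few sentences of text, with no new data. The downside is that with about 12 clinicians in 3 agencies the intervals will probably be wide, and the contrasts may have to carry a post hoc label.
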